1. OBJECTIVES

1.1 Overview

The Histiocytoses are a group of rare neoplastic diseases involving histiocytes. Langerhans Cell Histiocytosis (LCH), the most common of the group, is a disease caused by clonal proliferation of Langerhans cells that is characterized by a spectrum of varying degrees of organ involvement and dysfunction. Treatment of LCH is risk-adapted; patients with single lesions may respond well to local treatment, whereas patients with multi-system disease and risk-organ involvement (hematopoietic, liver, spleen) require more intensive therapy. While survival for patients without organ dysfunction is excellent, mortality rates for patients with organ dysfunction may reach 30 to 40%. For patients with low-risk disease, while cure is almost universal, disease reactivation rates are in excess of 30%. Related disorders, including Juvenile Xanthogranuloma (JXG), Rosai Dorfman Disease (RDD), Erdheim Chester Disease (ECD), Histiocytic Sarcoma (HS), and Interdigitating Dendritic cell Sarcoma/Histiocytosis (IDCMH) share some histopathologic and clinical features with LCH. There is currently no established therapy for any of these entities. Thus, new treatments are needed. Nucleoside analogues such as cladribine and cytarabine have proven to be effective in the management of Histiocytoses. More recently, clofarabine has proven to be effective in patients with refractory LCH and LCH-related disorders, thus suggesting that this newer nucleoside analogue should be investigated. In this Phase II study we are proposing to evaluate the efficacy of clofarabine in participants with recurrent or refractory LCH. In a separate stratum, we aim to register participants with histiocytic diseases other than LCH who require systemic therapy to accumulate experience with clofarabine in this rare patient population.

1.2 Study Design

This is a phase II efficacy study of clofarabine in patients with recurrent or refractory Langerhans Cell Histiocytosis (LCH) and LCH-related disorders that require chemotherapy.

1.3 Primary Objective

To estimate the response rate of participants with recurrent or refractory LCH to clofarabine.

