13.3 Study Design/Endpoints

The primary endpoint within each stratum will be the proportion of responders. A responder is defined as an eligible, evaluable participant who achieves either complete resolution or regression of disease, i.e., their disease gets "Better" per section 9.1, as the best overall response at any time up to and including the End of Cycle 2 assessment, which must be completed on Day 28 of Cycle 2 +/- 7 days, and must be completed prior to starting Cycle 3.

Secondary endpoints are:

- a) Progression-free survival (PFS), where time to event for PFS is the time from study enrollment until the time of first occurrence of new lesions, progressive disease, or death from any cause, or until last contact if no event occurs;
- b) Overall survival (OS), calculated as the time from enrollment until death or last contact;

CONFIDENTIAL

This document is confidential. Do not disclose or use except as authorized.

- c) Feasibility, which is assessed by the proportion of patients who experience a toxicity-event. Participants who have clofarabine stopped because of toxicity concerns will be considered to have experienced a toxicity-event. Otherwise, participants who complete therapy or who are removed from protocol therapy for reasons related to disease progression, second malignancy or death unrelated to protocol therapy will be considered to have successfully tolerated treatment; and,
- d) The proportion of participants reporting grades 3-4 toxicity, for each CTCAE v4.0 toxicity code.

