13.5 Monitoring Rules

The study will be referred to the DSMC for review of dosing and toxicity at the first occurrence of a toxic death.

A Simon's two-stage group sequential design will be used to determine if there is sufficient evidence of efficacy to warrant further investigation of clofarabine.

Rule A - Two-stage stopping rule for response in Stratum 1

Stage 1: Accrue 13 evaluable participants. If 7 or fewer respond, then there is insufficient evidence to support further study of clofarabine in this cohort, and the study will be closed to further accrual. We would also close the trial if it became apparent prior to the accrual of all 13 that we would never achieve the 8 responders. If 8 or more out of 13 are responders, then proceed to stage 2.

Stage 2: A total of 20 evaluable patients will be studied. If 13 or fewer respond, then there is insufficient evidence to support further study of clofarabine in this cohort. If 14 or more are responders, then there is sufficient evidence to warrant further investigation of clofarabine within this cohort.

This rule has 91% power to detect a 27% difference (53% under the null to 80% under the alternative), with $\alpha = 0.093$. If the response rates were actually higher, there would be even greater power to detect a 27% difference, for example 63% versus 90%.

Rules for monitoring for toxicity associated with chemotherapy

The study will be monitored to ensure the therapy can be delivered as planned ('chemotherapy feasibility'). Toxicities will be graded according to CTCAE version 4.0. Unacceptable toxicity will be defined as grade 5 toxicity and Grade 3 or 4 non-hematological toxicity that are possibly, probably, or definitely related to Clofarabine, with the specific exceptions of the following Grade 3 toxicities: anorexia, weight loss, nausea, vomiting, fatigue, mucositis, diarrhea, fever, electrolyte/metabolic abnormalities, menorrhagia, and

CONFIDENTIAL

This document is confidential. Do not disclose or use except as authorized.

infection. Because all patients, regardless of stratum, receive the same treatment with the standard dose of clofarabine (25 mg/m²/d), the stopping rule for toxicity will be applied to the overall cohort, i.e., combining Stratum 1 and Stratum 2. The toxicity monitoring rule will be applied to the first 25 evaluable participants, as this will provide sufficient evidence of safety/feasibility for the balance of the trial's accrual.

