13.6 Statistical Methods to Address Objectives

Objective 1.3 - Monitoring Rule A will be used to address primary objective 1.3. The analysis will include all evaluable Stratum 1 participants. In addition, a 95% confidence interval will be placed on the response rate.

Secondary Objective 1.4.a – Descriptive analyses using the methods of Kaplan and Meier (with standard errors per Peto) will be performed to calculate the PFS and OS within each stratum and overall. Lifetables will also be constructed.

Secondary Objective 1.4.b – Monitoring Rule B will be used to address secondary objectives 1.4.b and 1.4.c. In addition, a descriptive tabulation of the proportion of participants reporting grade 3 and higher toxicity, separately by stratum (1 and 2) and by CTC toxicity code, will be generated for all evaluable patients. A given participant will be counted only one time per toxicity code at the maximum grade regardless of the number of times that participant experienced the toxicity.

Secondary Objective 1.4.c – Within Stratum 2 and within subgroups of Stratum 2, we will calculate the proportion of evaluable patients who are responders, and place 95% confidence intervals on these proportions. A descriptive tabulation of the proportion of participants reporting grade 3 and higher toxicity, by CTC toxicity code, will be generated for Stratum 2 patients. A given participant will be counted only one time per toxicity code at the maximum grade regardless of the number of times that participant experienced the toxicity.

CONFIDENTIAL

This document is confidential. Do not disclose or use except as authorized.

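### The primary aim is to estimate the Stratum 1 response rate, but the implied estimate, x/n, ignores Rule A's early stopping and, averaged over all trial outcomes, is biased low by about 4.5 points at a true rate of 53% and 0.4 points at 80%

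*Combined protocol and SAP*

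**What the plan says.** Section 1.3 makes estimation the primary objective: "To estimate the response rate of participants with recurrent or refractory LCH to clofarabine". Section 13.3 defines the endpoint: "The primary endpoint within each stratum will be the proportion of responders". Section 13.6 addresses objective 1.3 through Rule A on all evaluable Stratum 1 participants, and continues: "In addition, a 95% confidence interval will be placed on the response rate". It names neither a point estimator nor an interval method, so responders over evaluable participants (x/n) is the natural reading.

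Section 13.5 makes the sample size depend on the results in two ways. The first is the stage 1 boundary: "Stage 1: Accrue 13 evaluable participants. If 7 or fewer respond, then there is insufficient evidence to support further study of clofarabine in this cohort". The second is curtailment within stage 1: "We would also close the trial if it became apparent prior to the accrual of all 13 that we would never achieve the 8 responders". Once stage 1 succeeds, "Stage 2: A total of 20 evaluable patients will be studied".

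Section 13.4 requires every evaluable participant to be assessed for response. Response is read at the End of Cycle 2 assessment (section 13.3). No pause in accrual is described while responses are awaited.

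**The concern.** When a sample ends because the results so far are poor, x/n is not an unbiased estimate of the response rate. Under the curtailment clause every failed stage 1 ends on a non-responder, which lowers x/n further. A trial that does well early goes on to 20, where its good start is diluted by later participants; a trial that does badly early gets no such correction. Averaged over both branches, x/n is too low.

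This matters because estimation is the stated primary aim, and section 14 promises a final report whatever the outcome. In a rare disease, with at most 20 evaluable participants planned, the reported rate could well serve as a reference figure for later trials. An estimator chosen after an early stop would look post hoc.

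**Working it through.** **Inputs** (section 13.5 unless stated): stage 1 n = 13, continue at 8 or more; total n = 20, success at 14 or more; null rate 53%, alternative 80%; stated alpha 0.093 and power 91%; accrual 10 per year (section 13.2); 28-day cycles, with delay to day 42 allowed (section 5).

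**Step 1. Reproduce the plan's figures.** P(success) = sum over x1 = 8 to 13 of P(Bin(13,p) = x1) × P(Bin(7,p) ≥ 14 − x1). This gives 0.0932 at p = 0.53 and 0.9085 at p = 0.80, matching the stated 0.093 and 91%. Curtailment in stage 1 changes neither.

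**Step 2. The early-stop branch.** Eight of 13 becomes unreachable at non-responder number 13 − 8 + 1 = 6. The trial stops at participant m (m = 6 to 13), with x = m − 6 responders, with probability C(m−1, 5) × p^(m−6) × (1−p)^6. The reported rate is (m − 6)/m, which never exceeds 7/13 = 53.8%.

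**Step 3. The stage 2 branch.** The mean of x/n is (E[X1 | X1 ≥ 8] + 7p)/20, where X1 is the stage 1 responder count.

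**Step 4. Combine**, with nobody pending at the stop:

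| True rate | P(stop in stage 1) | Mean x/n if stopped | Mean x/n if stage 2 reached | Overall mean | Bias (points) |
|---|---|---|---|---|---|
| 53% | 0.630 | 40.4% | 62.3% | 0.630×40.4 + 0.370×62.3 = 48.5% | -4.5 |
| 60% | 0.426 | 42.9% | 66.2% | 0.426×42.9 + 0.574×66.2 = 56.3% | -3.7 |
| 70% | 0.165 | 45.5% | 72.6% | 0.165×45.5 + 0.835×72.6 = 68.1% | -1.9 |
| 80% | 0.030 | 47.3% | 80.6% | 0.030×47.3 + 0.970×80.6 = 79.6% | -0.4 |

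Over all true rates the largest bias is -4.6 points, near 48.5%.

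**Step 5. How much is due to curtailment.** If all 13 are always completed, the bias is -1.9 at 53% and -0.3 at 80%; the largest is just under 2 points, near 57%.

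**Step 6. Pending participants.** Two 28-day cycles take 56 days, so at steady accrual (an assumption) 10 × 56/365.25 = 1.5 participants would be pending; with cycle 1 extended to day 42, 10 × 70/365.25 = 1.9. If 1, 2 or 3 pending participants are completed and counted, the bias at 53% is -3.65, -2.97 or -2.42 points.

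**Step 7. The unbiased estimate.** Among all outcome sequences that end at the observed result, take the fraction whose first participant is a responder. With nobody pending:

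- Stop at m: C(m−2, 5)/C(m−1, 5) = (m−6)/(m−1) = x/(m−1). For 5/11, 45.5% becomes 5/10 = 50.0%.
- After stage 2: sum of C(12, x1−1) × C(7, x−x1) divided by sum of C(13, x1) × C(7, x−x1), over x1 = 8 to 13. This gives 67.6% for 13/20, 70.7% for 14/20, and exactly x/20 from 15/20 upward.

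Its mean equals the true rate. Its root mean squared error is below that of x/n at the rates checked from 50% to 90%: 0.152 against 0.158 at 53%, 0.139 against 0.154 at 60%, and 0.117 against 0.135 at 70%.

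**The case against.** **The bias is small where the sponsor hopes to be.** It is 0.4 points at 80%, and even 4.5 points is minor beside a root mean squared error of 0.158 at 53%. This stands, and it limits the weight of the point.

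**The largest figure assumes conduct that the protocol does not describe.** Sections 13.4 and 13.6 imply that pending participants would be assessed and counted, so 4.5 points is the upper end at 53%. This stands.

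**A reader might infer that a completed trial ending with 8 to 13 of 20 reports a rate that is systematically too low.** The design does not support that. Given that stage 2 is reached, x/n averages 62.3% at a true 53%, about 9 points high. Within 8 to 13 of 20 it averages 58.8% at a true 53% and 60.3% at 60%; it is low there only at higher rates (62.1% at 70%). The claim is therefore confined to the average over all outcomes.

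**The unbiased estimate has costs.** For poor stage 2 results it moves far from x/n: 10/20 gives 62.9%, and 8/20 gives 8/13 = 61.5%, so all seven stage 2 non-responders are ignored. Given that stage 2 is reached at a true 53%, it averages 67.4%, further from the truth than x/n; after an early stop it still averages only 44.6%. Finishing stage 2 at 10/20 or worse is unlikely: the sum over x1 = 8 to 10 of P(Bin(13,p) = x1) × P(Bin(7,p) ≤ 10 − x1) is 0.039 at 53% and 0.025 at 60%. The objection still rules out replacing x/n.

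**A reader might also infer that the error rates or the interval fail.** Alpha and power reproduce. If a Clopper-Pearson interval is assumed (the plan names no method), coverage under the curtailed rule is 96% to 98% at the true rates checked from 40% to 80%.

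**Conclusion.** The point holds as a statement about bias averaged over all trial outcomes. The plan sets estimation as its primary aim, implies x/n, and makes no allowance for a stopping rule that biases x/n low. With nobody pending, the size runs from 4.5 points at the null rate to 0.4 points at the alternative. At 53% it falls to roughly 3.7 to 2.4 points if one to three pending participants are counted, and to 1.9 if there is no curtailment. The calculation assumes independent participants with a common response rate, and outcomes that become known in order of enrolment. The source is the early-stop branch. Nothing here questions the cut-offs of Rule A or the decision it produces. It is a cheap improvement to the reporting of the primary result.

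**What to change.** In section 13.6, Objective 1.3:

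- State that x/n is reported as the observed response rate.
- Add, as a prespecified supplementary estimate, the uniformly minimum-variance unbiased estimate for the design actually followed, computed by path counting. Say that it equals x/(m−1) only when the trial stops at participant m with nobody pending.
- State that if participants are pending at a stage 1 stop, they are completed and included, as sections 13.4 and 13.6 already require, and that the supplementary estimate is computed for the actual sequence including the overrun. Fix that calculation in advance, because with an overrun more than one unbiased estimate exists. Simply adding the pending participants to the numerator and denominator of x/(m−1) is not unbiased: at 53% it overshoots by about 1.2 points with two pending and 1.6 with three.
- Note that the two estimates can differ widely after a poor stage 2, which is why both are shown.

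The cost is a few sentences and a few lines of code. No participants, procedures or cut-offs change.

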1.4 Secondary Objectives

- a) To estimate the progression-free survival and overall survival of participants with recurrent or refractory LCH to clofarabine.
- b) To determine if clofarabine therapy can be delivered as planned ('chemotherapy feasibility'), and to describe toxicities of clofarabine in participants with LCH.
- c) To describe the toxicities and responses to clofarabine treatment in participants with LCH-related disorders.

CONFIDENTIAL

This document is confidential. Do not disclose or use except as authorized.

2. BACKGROUND

2.1 Study Disease

Langerhans Cell Histiocytosis (LCH) is a proliferative disorder of activated Langerhans cells (LC) with highly variable biological behavior and clinical severity.¹ The histopathology of the lesion is uniform regardless of the clinical severity of the disease, and consists of collections of LC, interdigitating cells and macrophages, accompanied by T lymphocytes with variable numbers of multinucleated giant histiocytes and eosinophils.² The pathogenesis of LCH is poorly understood. Because LCH has been demonstrated to be a monoclonal disease it may be considered a neoplastic disorder.³ However, different patterns of clinical involvement indicate other pathogenetic mechanisms. The occurrence of spontaneous remission⁴ and the benign histopathological appearance of the lesions in LCH suggest a reactive clonal disorder rather than a malignant process, at least in some cases. Langerhans cells, like other dendritic cells, have a critical role in the immune system, and it has been suggested that LCH could be the result of immune dysregulation. Although no consistent immunologic abnormalities have been described, there is increasing evidence that LCH may be the result of an uncontrolled and abnormal proliferation of Langerhans cells secondary to either immune dysregulation or following exposure to a yet undetermined stimulus.⁵ In order to reconcile the clonal origin of the pathologic Langerhans cells with the evidences for immune dysregulation, a hypothesis has emerged that proposes that the monoclonal expansion seen in LCH could represent a host response to chronic antigenic stimulation. Under conditions of chronic stimulation, dominant clones of dendritic cells might emerge. These clones might still retain some ability to respond to normal immune regulatory loops, as exemplified by the therapeutic effect of cyclosporine.

Treatment of LCH

The treatment of LCH over the years has reflected the changing concepts of the disease process. Indeed, the difficulties in developing more effective therapies are linked to the deficiencies in the understanding of the pathogenesis of LCH. Retrospective studies of Lahey⁶ and Komp et al⁷ showed that, although many organs can harbor proliferating Langerhans cells, only if organ function were disrupted was such involvement of prognostic significance. Patients could then be stratified into different risk categories based on the extent of their disease and the degree of organ dysfunction. Two large cooperative trials^{8,9} later confirmed those findings, and also identified a subgroup of patients (defined by age > 2 years and absence of organ dysfunction) with an excellent prognosis despite multi-system involvement. Treatment for patients with LCH is currently risk-adapted. Patients with single-system disease confined to a single site usually require only local therapy or observation. Patients with more extensive disease (multiple bone lesions or multiple lymph nodes) usually require systemic therapy. The best therapeutic option in these cases has not been defined, and responses have been observed with short courses of steroids with or without the addition of chemotherapeutic agents.¹⁰ The treatment recommended by the Histiocyte Society for this group of patients includes a 6-week induction with prednisone and vinblastine, followed by continuation treatment with pulses of the same agents every 3 weeks. The prognosis for this group of patients is usually excellent, although approximately 30% of the patients will experience disease reactivations that continue to respond to treatment.

CONFIDENTIAL

This document is confidential. Do not disclose or use except as authorized.

Five major cooperative trials have addressed treatment for patients with multi-system disease: the Italian AIEOP-CNR-HX 83 protocol,⁸ the Austrian/German DAL-HX 83/90 protocol,⁹ and the three trials of the Histiocyte Society (LCH-I,¹¹ LCH-II,¹² and LCH-III protocols). All these protocols were risk-adapted, and were based in different combinations of prednisone, vinblastine, etoposide, methotrexate and 6-mercaptopurine. In all those studies, survival rates are in excess of 90% for patients with multi-system disease without involvement of risk organs. For this group of patients, the treatment currently recommended by the Histiocyte Society is a 12-month regimen with prednisone and vinblastine. Involvement of the risk organs carries the worse prognosis. This high-risk group of patients is characterized by early age at presentation (usually < 2 years), and different degrees of liver, spleen, hematopoietic, and lung involvement. Patients respond poorly to treatment, and mortality rate is approximately 40%.

Treatment of Recurrent LCH

Disease reactivation is common in patients with LCH, and two groups of patients are identified:

- a) Patients with “low-risk” disease. Includes patients with reactivation of multifocal bone disease or low-risk multisystem disease (without risk organ involvement); disease reactivations occur in approximately one-third of patients, and they usually respond well to second-line therapy. Many regimens have been described, including oral 6-mercaptopurine and methotrexate,¹³ indomethacin,¹⁴ bisphosphonates,¹⁵ and cladribine.¹⁶
- b) Patients with “high-risk” disease. This high-risk group is characterized by the presence of risk organ involvement, and poor response to standard treatment. Mortality is high, and recent data suggest that an intense regimen with cladribine and high-dose cytarabine may be effective.^{17,18} Allogeneic hematopoietic stem cell transplantation has also been proposed for those cases.¹⁹

Treatment of Recurrent or Refractory LCH with Nucleoside Analogues

Treatment of LCH with 2-CdA

The enzyme adenosine deaminase (ADA) has an essential role in the intracellular degradation of purine nucleosides derived from DNA breakdown. In ADA deficient cells, deoxyadenosine is metabolized by deoxycytidine kinase (dCk), resulting in increased cellular concentrations of deoxyadenosine mono-, di-, and tri-phosphates (dAMP, dADP, and dATP), that are toxic to the cells.²⁰ 2-chlorodeoxyadenosine (2-CdA, cladribine) is a purine analog resistant to ADA but not to dCk. This results in accumulation of chlorinated deoxyadenosine nucleotides that may be eventually incorporated into the DNA of dividing cells, which results in induction of arrest in the S phase of the cell cycle,²¹ and activation of the apoptotic pathway. However, in contrast with conventional antimetabolites, 2-CdA is extremely toxic to mature, non-dividing lymphocytes. High concentrations of deoxynucleotides might interfere with the repair of DNA breaks, thus initiating the process of programmed cell death.²² In children, 2-CdA has mainly been used in the treatment of AML, where responses of up to 59% are obtained as a single agent.²³ Normal mature lymphocytes and monocytes express high levels of dCk.²⁴ In vitro studies have shown that 2-CdA is a highly selective anti-monocyte agent, which causes decreased monocyte function and viability and decreased IL-6 secretion.²⁵ Because tissue histiocytes are derived from the same stem cells as circulating monocytes, 2-CdA has been investigated for the treatment of patients with histiocytic disorders. Excellent clinical responses, with an overall response rate of 82% have been reported in adults with recurrent LCH.²⁶ In children, the role of 2-CdA has been explored in two scenarios.

CONFIDENTIAL

This document is confidential. Do not disclose or use except as authorized.

- a) For patients with low-risk disease reactivation, cladribine has shown to induce responses in > 90% of the patients, although further reactivations still occur.^{16,27-29} One additional benefit of cladribine is its effect on CNS disease (a common complication of LCH).^{30,31} A major limitation with the use of cladribine is its limitation to a short treatment course; more than 4 or 6 courses of treatment are associated with prolonged myelosuppression, causing a clinical picture similar to myelodysplasia.
- b) For patients with high-risk disease, cladribine as a single agent has little effect,²⁸ and a more intensive regimen is needed. The combination of high-doses of cladribine (9 mg/m²/day x 5 days) with cytarabine (1 gr/m²/day x 5 days) has induced complete responses in patients with refractory disease.^{17,32} While this treatment seems to be effective, it is associated with high morbidity, with treatment-related mortality in excess of 20%.

Treatment of LCH-related Disorders

Several rare entities that occur in children and adults are defined by the proliferation and/or accumulation of cells of the histiocyte lineage but differ from LCH in histology, immunohistochemistry and clinical behavior.

Rosai-Dorfman Disease (RDD), also known as Sinus Histiocytosis with Massive Lymphodeopathy, is a disease of children and young adults that is characterized by proliferation of S100 positive, CD1a negative histiocytes. RDD most often presents as massive bilateral cervical lymphadenopathy, sometimes associated with symptoms of systemic inflammation. Many RDD patients experience a relapsing/remitting course but one that is ultimately benign and self-resolving. For the subset of RDD patients who have extranodal involvement or nodal disease with risk for life threatening complications, systemic treatment is indicated. A variety of chemotherapy and immunomodulatory agents have been tried with variable success. There is currently no standard treatment approach. Cladribine³³ and clofarabine³⁴ have shown encouraging activity in limited published experience in RDD.

Juvenile Xanthogranuloma (JXG) is a rare, benign histiocytic disorder that most often presents in infancy as single or multiple skin nodules. Biopsy shows Touton giant cells that are negative for CD1a and langerin (and usually S100 as well), but positive for Factor XIIIa, fascin, CD14, CD68, and CD163. Ocular, CNS, liver/spleen and lung involvement occurs in a small minority of JXG cases. Treatment of extra-cutaneous JXG with LCH- based regimens,³⁵ cladribine³⁶ and clofarabine³⁴ has met with some success.

Erdheim-Chester disease (ECD) is a rare non-Langerhans histiocytic disorder most commonly characterized by multifocal osteosclerotic lesions of the long bones demonstrating sheets of foamy histiocytes on biopsy with or without histiocytic infiltration of extraskelatal tissues. The pathogenesis of Erdheim-Chester disease (ECD) is poorly understood. Attempts to establish clonality have produced varied results, and although occasional clonal cytogenetic aberrations have been identified, none are characteristic or diagnostic.³⁷ An activating point mutation of the BRAF isoform of RAF (BRAF V600E) is identified in approximately 50 percent of cases of ECD and several case series have reported clinical responses to the BRAF inhibitor vemurafenib.³⁸⁻⁴⁰ There is no standard treatment regimen for patients with symptomatic ECD, and patients should be encouraged to enroll in a clinical trial. Most patients are treated with conventional or pegylated interferon-alpha rather than systemic chemotherapy.⁴¹ The BRAF inhibitors vemurafenib or dabrafenib are reasonable options for patients with a BRAF V600E mutation who fail to respond to or cannot tolerate interferon-alpha. Systemic chemotherapy agents such as cladribine,

CONFIDENTIAL

This document is confidential. Do not disclose or use except as authorized.

methothrexate and cyclophosphamide may be effective but are poorly studied.^{42,43} The optimal treatment of patients who fail interferon and who are not candidates for or do not respond to BRAF inhibitors remains unclear. Given the activity of clofarabine in other histiocyte disorders additional study in ECD is warranted.

Histiocytic sarcoma (HS) is an extremely rare and generally aggressive malignancy typically comprised of non-cohesive, large cells that are polygonal or ovoid with spindling and abundant eosinophilic cytoplasm. Occasionally, the neoplastic cells can have a foamy appearance, but this is not nearly as pronounced as in Erdheim-Chester disease. There is typically a prominent inflammatory infiltrate, but necrosis is minimal. Hemophagocytosis may occasionally be present. The malignant cells usually expressed CD68, lysozyme, CD4, and CD 163. CD1a, S100, T and B-cell markers aside from CD4, and epithelial markers are usually absent. Birbeck granules are lacking.⁴⁴ HS can occur as a de novo disease or concomitant with or subsequent to other hematologic neoplasms including follicular lymphoma, myeloid leukemias, and germ cell tumors. Patients with localized disease have a favorable prognosis after surgical resection, radiation, or both.⁴⁵ Unfortunately, patients with disseminated disease have a very poor prognosis. Patients are often treated with regimens used in aggressive lymphomas such as CHOP and ICE but response rates are poor.⁴⁶ There are anecdotal reports of responses to agents such as cladribine⁴⁷ and alemtuzumab⁴⁸ but new therapeutic options are desperately needed. There are reports of responses with clofarabine in HS³⁴ and given the general lack of other effective options further study is warranted.

Interdigitating dendritic cell sarcoma (Interdigitating cell malignant histiocytosis or IDCMD) is an extremely rare neoplasm of unknown cause. The neoplastic cells are usually found in the paracortical region of lymph nodes and are consistently positive for S 100 and vimentin. Fascin is also often positive. Expression of CD68, lysozyme and CD45 is variable. CD1a and CD207 are negative and the Ki67 proliferative index is low. The majority of patients have localized disease at diagnosis. Isolated nodal disease makes up 47% of reported cases, isolated extranodal disease 25% and combined nodal and extranodal 28%.⁴⁹ Extranodal sites include the liver, spleen, tonsils, bone marrow, lungs, skin, soft tissue, bowel, and bladder. Patients with metastatic disease have a poor outcome (38% survival at 1 year) though patients with localized disease can do well (85% survival at 1 year). The median survival for patients with metastatic disease is 9 months (0.25 – 72 months).⁴⁹ Patients with metastatic disease are usually treated with chemotherapy. A range of chemotherapy treatments have been reported but responses are often absent/short-lived, and outcomes remain poor. Chemotherapy regimens reported include ABVD (doxorubicin, bleomycin, vinblastine, dacarbazine); CHOP (cyclophosphamide, doxorubicin, vincristine and prednisolone); docetaxel + gemcitabine; IE (ifosfamide and eoposide).⁴⁹ Given the poor outcome of patients with metastatic diseases inclusion in a clinical trial with a new therapeutic agent known to have activity in histiocyte disorders is appropriate.

